1.2. STUDY RATIONALE

This study is being conducted to determine the safety and efficacy of Raplixa for achieving hemostasis in pediatric subjects undergoing hepatic, renal, soft tissue, spinal, or vascular surgery. Raplixa and the RaplixaSpray device are approved for use in adults, but have not previously been evaluated in pediatric subjects. Topical hemostats, Recothrom® and Tisseel®, have previously been evaluated and approved by regulatory agencies for use in pediatric patients. The safety profile of these products in pediatric patients was similar to that in adult patients and there was no observation of enhanced immunogenic responses in the pediatric population. As Raplixa is a pharmacologically active topical hemostat as are Recothrom® and Tisseel®, it is expected that Raplixa will have a similar safety, efficacy, and non-immunogenic profile in pediatric patients as Raplixa treatment in the adult population.

1.3. STUDY POPULATION

Pediatric subjects will be treated in this study, with the 2 oldest age groups enrolled simultaneously first. Subjects will be segregated into 4 age groups which are generally consistent with the European Medicines Agency (EMA) (EMEA, CPMP/ICH/2711/99) and the FDA (ICH E11, December 2000) requirements:

- Adolescents (11 to less than 18 years).
- Children (2 years to less than 11 years).
- 6 months to less than 2 years.
- Birth (\geq 36 weeks gestational age at birth) to less than 6 months.

2. TRIAL OBJECTIVES AND PURPOSE

The objective of the study is to evaluate the efficacy and safety of Raplixa plus gelatin sponge, as compared to gelatin sponge alone, for achieving hemostasis in pediatric subjects undergoing hepatic, renal, soft tissue, spinal, or vascular surgery.

3. TRIAL DESIGN

3.1. TYPE/DESIGN OF TRIAL

This is a Phase 2, multicenter, randomized, single-blind, controlled trial comparing the efficacy and safety of Raplixa in combination with an absorbable gelatin sponge to gelatin sponge alone, in pediatric subjects undergoing hepatic, renal, soft tissue, spinal, or vascular surgery. The study will enroll approximately 87 subjects at up to 25 sites in the US.

Informed consent will be obtained from parents/guardians for each subject before any protocol-related assessments or procedures are conducted. Subjects 7 years and older, or of an appropriate age as defined by local regulations, may be required to provide assent to participate in the study.

Eligible subjects will be randomized in a 2:1 ratio to receive treatment with Raplixa in combination with an absorbable gelatin sponge (active group; R+G) or gelatin sponge alone (control group; G) when an appropriate target bleeding site (TBS) is identified. Subjects who are not treated with study drug will be withdrawn from the study and may be replaced.

Reasons for not receiving study drug include, but are not limited to; lack of an appropriate TBS for time to hemostasis (TTH) evaluation, severe bleeding, or a change in surgical procedure that renders the subject ineligible, after the subject has been randomized.

Subjects will be enrolled across 4 different age groups, with the 2 oldest age groups enrolled simultaneously: 1) 11 years of age to less than 18 years of age; 2) 2 years of age to less than 11 years of age; 3) 6 months of age to less than 2 years of age; or 4) ≥ 36 weeks gestational age at birth to less than 6 months of age. Following completion of Visit 5, Day 30, for 6 subjects treated with Raplixa plus gelatin sponge within 1 of the 2 oldest age groups, the Independent Data Monitoring Committee (IDMC) will review all available safety data and verify that the observed safety profile supports continued subject enrollment. Study enrollment will not be stopped during the IDMC review. After the IDMC review, this body will notify the study team if the safety assessment shows that there is a favorable benefit-to-risk outcome to continue enrollment in the two older cohorts, and whether it is acceptable to initiate sequential enrollment in the two lower age cohorts.

During a surgical procedure on Day 1 (Visit 2), subjects will be initially treated with up to one vial of Raplixa (1.0 g) plus gelatin sponge or gelatin sponge alone at the TBS. The TTH will be assessed every 30 seconds for up to 5 minutes. Bleeding appropriate for TTH evaluation is defined as mild to moderate bleeding, either on its own or remaining after brisk/severe bleeding has been controlled by standard surgical modalities. Subjects may be retreated with their assigned treatment as necessary during the 5-minute TTH assessment period, with up to a maximum of 2 vials of Raplixa (2.0 g) in total (for target and non-target bleeding sites). Rescue treatment may be administered at the TBS or OBS if necessary in a

tiered approach after the 5-minute TTH assessment period has elapsed, at the discretion of the Investigator (see Section 5.5 for details).

[figure not shown]
For subjects who are randomized and receive Raplixa, at any time after hemostasis has been achieved at the TBS and the 5-minute TTH assessment period has elapsed, the remaining Raplixa may be used at additional appropriate OBS that are part of the primary surgical procedure. Importantly, the remaining Raplixa should not be used on OBS until after the 5-minute TTH assessment period has elapsed in order to ensure that adequate Raplixa is available to use in the event of re-bleeding from the TBS. The amount of Raplixa applied and the incidence of hemostasis achieved at OBS will be recorded; however, the primary efficacy analysis will not include hemostasis data from the OBS.

Subjects will undergo a safety evaluation consisting of a targeted physical examination and clinical laboratory tests on Day 2 (Visit 3). If the subject's surgery was performed as an outpatient procedure, the Visit 3 assessment may be conducted over the phone with the physical examination conducted and laboratory tests collected prior to discharge on Day 1. Safety evaluations will also be performed on Day 7 (Visit 4), via telephone, if the subject has been discharged, and on Day 30 (Visit 5; End of Study visit). Immunogenicity samples (monitoring for anti-thrombin antibodies) will be collected and analyzed at baseline and at Day 30 for all treated subjects, except subjects who are less than 6 months old. Additional monitoring for anti-fibrinogen antibodies will be limited to subjects found positive for anti-thrombin antibodies and subjects with unexplained bleeding or clinical suspicion of bleeding related to antibody formation.

A subject's study participation ends after the Day 30 visit. However, should a subject return to the investigator between Day 30 and Day 90 for routine follow-up visits (not scheduled for the purpose of the study), the investigator will record any update in the subject's safety information and report such information to the Sponsor using the data collection forms provided.

3.2. SCHEMATIC DIAGRAM OF TRIAL DESIGN

Figure 1 Study Schema and TTH Assessment on Visit 2 (Day 1)

3.3. ENDPOINTS

The study endpoints are:

Safety

- Overall safety, as determined by the incidence, severity and relationship of adverse events (AEs) with a study product or a study procedure, clinical laboratory abnormalities, estimated rates of immunogenicity (monitoring for anti-thrombin antibodies) collected and analyzed at baseline and at Day 30 for all treated subjects, except subjects who are less than 6 months old. Additional monitoring for anti-fibrinogen antibodies will be limited to subjects found positive for anti-thrombin antibodies and subjects with unexplained bleeding or clinical suspicion of bleeding related to antibody formation and post-surgery bleeding complications.

Efficacy

- Percentage/proportion of subjects who reach hemostasis from the first identified TBS within 4 minutes of study drug application.
- Restricted mean TTH (during the 5-minute TTH assessment period).
- Through to Visit 5, EOS visit:
 - Use of alternative hemostatic agents on the TBS.
 - Volume of transfused blood (whole blood, fresh frozen plasma (FFP), cryoprecipitate, platelets, or packed red blood cell (PRBC)).
 - Incidence of re-operation for bleeding at the TBS.

3.4. MEASURES TO MINIMIZE/AVOID BIAS

3.4.1. Blinded Study

Sealed, blinded envelopes will be provided by an external statistician, who also holds the randomization lists during the study. Only after the surgeon has identified an appropriate TBS, in the operating room, and notified the study coordinator that the site has been identified and he/she is ready for the treatment designation, will the Investigator/designee open a randomization envelope which corresponds with the type of surgical procedure the subject is undergoing. The time of randomization is subsequently recorded. If a randomization envelope has been opened and the subject does not receive the assigned study drug, this envelope may not be used for another subject.

4. SUBJECT POPULATION

The study will enroll subjects undergoing one of the following surgical procedures:

1. Hepatic Surgery

Hepatic wedge resection or anatomic resection of 1 to 5 contiguous hepatic segments, which may be combined with surgical procedures involving the pancreas, gall bladder, bile duct or intestines. Subjects undergoing living-related liver donation are also eligible.

2. Renal Surgery

Nephrectomy associated with diffuse oozing from the retroperitoneal wall.

3. Soft Tissue Surgery

The TBS will be identified during the soft tissue dissection related to the primary operative procedure. Primary operative procedures include but are not limited to: lower anterior resections, abdominal perineal resections, donor skin graft site (split-thickness-meshed, split-thickness-non-meshed, full thickness, and composite graft) in limited burn patients (up to 40% total body surface area [TBSA]), breast mass excision, cleft lip repair, and hernia repair.

Appropriate soft tissue types will include but will not be limited to: loose areolar tissue, fat, lymphatic tissue/lymph node beds, and muscle. The TBS will not involve parenchymal, gastrointestinal or genitourinary soft tissue, cardiac, lung or brain tissue, as Raplixa has not yet been studied in these tissue types.

4. Spinal Surgery

Scoliosis surgery, cervical, thoracic, or lumbar discectomy, corpectomy, laminectomy, lateral or interbody fusion. Epidural bleeding typically described as oozing, flowing, or pulsatile, and normally requiring topical adjuncts to hemostasis is necessary to be considered eligible. The TBS may not be within a bony cavity or other confined area.

5. Vascular Surgery

All subjects undergoing vascular surgery should be systemically heparinized according to standard procedures. The clamp(s) should be removed to determine if an appropriate TBS with mild to moderate bleeding is present. The clamp(s) should remain off once a TBS is identified and during the treatment and assessment of TTH. If protamine reversal is indicated, it should occur after the 5-minute TTH assessment period is completed, unless a safety concern dictates that it should happen earlier. Appropriate vascular surgical procedures may include, but are not limited to: artificial graft (i.e., polytetrafluoroethylene [PTFE] or Dacron) for hemodialysis access (including revision procedures), hemangiomas, and vascular injuries (peripheral or abdominal). The TBS may not involve the heart or the vessels surrounding the heart.

4.1. NUMBER OF SUBJECTS

Approximately 87 subjects will be evaluated for efficacy and safety at up to 25 centers located in the US.

4.2. INCLUSION CRITERIA

Subjects may be included in the study if they meet all of the following criteria:

1. Subject age is \geq 36 weeks gestational age at birth (for infants) through < 18 years of age at time of treatment.
2. Subject's legal representative (parent or guardian) has signed an institutional review board (IRB)-approved informed consent document.
3. If a subject is \geq 7 years old, or appropriate age as defined by local regulations, the subject may be required to have signed an IRB-approved assent document.
4. Subject is scheduled to undergo one of the surgical procedures described in the protocol.
5. If female and of child-bearing potential, subject has a negative pregnancy test on the day of surgery (baseline).
6. If subject is a sexually active male or a sexually active female of child-bearing potential, subject agrees to use a medically accepted form of contraception from the time of consent to completion of all of the follow-up study visits.

During Surgery Inclusion Criteria

1. Presence of mild or moderate bleeding/oozing.
2. TBS surface area of ≤ 100 cm².
3. Subject has not received any whole blood, fresh frozen plasma (FFP), cryoprecipitate, or platelets within 24 hours prior to study drug. Packed red blood cell (PRBC) transfusions are allowed.
4. Subject has no intra-operative complication other than bleeding which, in the opinion of the Investigator, may interfere with the assessment of efficacy or safety.

4.3. EXCLUSION CRITERIA

Exclusion Criteria

Subjects will be excluded from the study if any of the following exclusion criteria apply prior to enrollment:

1. Gestational age of < 36 weeks at birth (for infants less than 6 months).
2. Subject has any clinically-significant congenital coagulation disorder (e.g., hemophilia A or B) that may interfere with the assessment of efficacy or pose a safety risk to the subject according to the Investigator.

3. Subject has baseline abnormalities of international normalized ratio (INR) > 2.5 or activated partial thromboplastin time (aPTT) > 100 seconds during screening that are not explained by current drug treatment (e.g., warfarin, heparin) or chronic disease state necessitating surgery (e.g., end stage liver disease).
4. Subject has aspartate aminotransferase (ASAT/AST) and alanine aminotransferase (ALAT/ALT) > 3 times the upper limit of reference range during screening, except for subjects undergoing liver resection surgery or with a diagnosis of liver disease where there is no upper limit for these analytes due to the nature of their disease.
5. Subject is unwilling to receive blood products or products derived from human blood
6. Subject has platelets < 100 x10⁹ PLT/L during screening, unless due to chronic disease state, e.g., liver disease/failure, necessitating surgery.
7. Subject has known antibodies or hypersensitivity to Raplixa or any of its components, other thrombin preparations, or coagulation factors.
8. Subject has known allergy to porcine gelatin.
9. Subject has medical, social, or psychosocial factors that, in the opinion of the Investigator, could impact subject safety or compliance with study procedures.
10. Subject is; 1) currently participating in another clinical study or 2) has participated in another clinical study within 30 days of screening or 3) plans to participate in a clinical study prior to completion of the 30-day follow-up period.

4.4. WITHDRAWAL CRITERIA

Subjects are free to withdraw consent and discontinue participation in the study at any time. If a subject decides to discontinue participation, he/she will be contacted in order to obtain information about the reason(s) for discontinuation and collection of any potential AEs. A subject's participation may be discontinued at any time at the discretion of the Investigator if the subject is uncooperative, major protocol violations or deviations from the treatment plan dictated by the protocol are identified, the Investigator feels that it is in the subject's best interest to be withdrawn from the study, the subject is lost to follow-up after multiple attempts at contacting the subject, or the study is terminated by the sponsor.

A clear, concise reason should be recorded in the electronic case report form (eCRF) for all discontinued subjects. Subjects discontinued from the study due to an AE should be followed until the AE has abated, or is felt to be clinically stable by the Investigator. Follow-up for these subjects may require additional tests or medical procedures as deemed appropriate by the Investigator, and/or referral to the general physician or a medical specialist. All study data from early withdrawals or discontinued subjects will be retained and, if appropriate, used in the final study analyses. Subjects withdrawn or discontinued from the study may be replaced if the statistical powering of the study is impacted.

It is imperative to obtain complete follow-up data for all treated subjects. Every attempt should be made to collect follow-up information except for those subjects who specifically

withdraw consent for release of such information. All procedures and laboratory specimens or tests requested for evaluation following administration of study drug should be carried out when possible, according the protocol. Subjects who are enrolled but not treated with study drug will be withdrawn from the study and may be replaced.

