target and non-target bleeding sites). Rescue treatment may be administered if necessary in a tiered approach at the TBS or other bleeding sites (OBS) with thrombin-containing hemostats permitted after all other treatment options have been attempted after the TTH assessment period has elapsed, at the discretion of the Investigator.

For subjects randomized to Raplixa, at any time after hemostasis has been achieved at the TBS, and the 5-minute TTH assessment period has elapsed, the remaining Raplixa may be used at additional appropriate OBS that are part of the primary surgical procedure. Importantly, the remaining Raplixa should not be used on OBS until after the 5-minute TTH assessment period has elapsed in order to ensure that adequate Raplixa is available to use in the event of re-bleeding from the TBS. The amount of Raplixa applied and the incidence of hemostasis achieved at OBS will be recorded; however, the primary efficacy analysis will not include hemostasis data from the OBS.

Subjects will undergo a safety evaluation consisting of a targeted physical examination and clinical laboratory tests on Day 2 (Visit 3). If the subject's surgery was performed as an outpatient procedure, the Visit 3 assessment may be conducted over the phone with the physical examination conducted and laboratory tests collected prior to discharge on Day 1. Safety evaluations will also be performed on Day 7 (Visit 4) via telephone, if the subject has been discharged, and on Day 30 (Visit 5; End of Study Visit). Immunogenicity samples (monitoring for anti-thrombin antibodies) will be collected and analyzed at baseline and at Day 30 for all treated subjects, except subjects who are less than 6 months old. Additional monitoring for anti-fibrinogen antibodies will be limited to subjects found positive for anti-thrombin antibodies and subjects with unexplained bleeding or clinical suspicion of bleeding related to antibody formation.

Number of Subjects:

The study will enroll a total of up to 87 subjects.

Diagnosis and Main Criteria for Selection:

The study will enroll subjects undergoing one of the following surgical procedures:

1. Hepatic Surgery

Hepatic wedge resection or anatomic resection of 1 to 5 contiguous hepatic segments, which may be combined with surgical procedures involving the pancreas, gall bladder, bile duct or intestines. Subjects undergoing living-related liver donation are also eligible.

2. Renal Surgery

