5.5. CONCOMITANT MEDICATIONS

Subjects may continue all normally prescribed medication regimens during this trial, and must notify the investigator when changes are made to their medication regimens. Medications will be coded using the WHO drug dictionary.

5.5.1. **Rescue Treatment**

If hemostasis is not achieved TBS during the 5-minute TTH assessment period, administration of additional study drug (no more than 2 vials of Raplixa [2.0 g] total), or other topical hemostats are permitted. If hemostasis cannot be achieved at an OBS or Raplixa is not indicated for use at the OBS, rescue treatment, if needed, should follow a tiered approach:

1. Additional study drug or surgical hemostatic measures (e.g., suture, cautery, and ligature) should be considered first.
2. Followed by thrombin-free topical hemostats.
3. Finally, thrombin-containing hemostats (recombinant or human plasma-derived products) may be administered, if needed.

A list of examples of thrombin-free and thrombin-containing hemostatic agents is provided in Table 2.

Table 2: Examples of Other Topical Hemostatic Agents

Thrombin-Free	Thrombin-Containing ^a
CoSeal™	CoStasis®/Vitage®/TM
Surgifoam™	Crosseal™
Ultrafoam™	Tisseel®
Gelfoam®	Fibrin sealant produced by the blood bank or in the operating room
Instat™	Evicle™
BioGlue®	Evithrom™
DuraSeal®	Recothrom®
Bone wax®	Surgiflo®
	Tachosil®
	Artiss®

a. Investigators should consider the use of products containing thrombin, only after other rescue alternatives fail.

5.6. **BLINDING**

Subjects will be randomized in a single-blinded manner. Randomization will be done in a 2:1 ratio (active:control).

5.6.1. **Blinding of Study Medications**

Study drugs will be blinded to study subjects but not to the Investigators, the study site personnel, or the Sponsor's study team.

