9. DATA COLLECTION

An electronic data capture (EDC) system will be used for this trial. All users will be trained on the technical features of the EDC as well as the content of the eCRF by qualified personnel prior to gaining access to the EDC. A User ID/Password will be granted after training. This ID is not to be shared amongst the study staff. All users must have a unique account to enter or review data. The eCRF should be filled out by the site within 48 hours after a visit. It is not expected that the eCRF will serve as source for any data collected in this trial. If there is a reason for a site to do so, it must be approved by MDCO and documented in the site files.

Prior to the database being locked, the investigator or designee will review, approve and sign/date each completed eCRF. This signature serves as attestation of the Investigator's responsibility for ensuring that all data entered into the eCRF are complete, accurate and authentic. After the end of the trial, a copy of the data will be provided to the site. This copy will contain the final data, an audit trail of activity on the data, and any queries and answers that were posted for data clarification.

A second data lock date will be set to ensure the capture of safety data from routine or unspecified visits after the Day 30 visit but before Day 90.

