10.1. SAMPLE SIZE

The sample size estimation is based on data from the completed Phase 3 trial (FC-004). Assuming the proportion of subjects achieving hemostasis within 4 minutes in R+G and G are 87% and 60% respectively, approximately 87 pediatric subjects (58 in R+G, 29 in G) will provide approximately 80% power to detect this difference at the one-sided significance level of 0.025 (equivalently, 2-sided significance level of 0.05) based on a chi-square test for 2 proportions.

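### Do the replacement rule and the differing counts of 87 undermine the all-randomized primary analysis?

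*Combined protocol and SAP*

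**What the plan says.** Section 4.4 has two replacement sentences. One is conditional on power: "Subjects withdrawn or discontinued from the study may be replaced if the statistical powering of the study is impacted". The other is not: "Subjects who are enrolled but not treated with study drug will be withdrawn from the study and may be replaced". Section 3.1 repeats the second, "Subjects who are not treated with study drug will be withdrawn from the study and may be replaced", and makes clear that non-treatment can arise after randomization. Sections 3.4.1, 5.6.2 and 10.2 bar the reuse of an opened envelope.

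The target of 87 is worded in several ways:
- Synopsis, Number of Subjects: "The study will enroll a total of up to 87 subjects".
- Section 3.1: approximately 87 enrolled.
- Section 4.1: "Approximately 87 subjects will be evaluated for efficacy and safety".
- Section 10.1: "approximately 87 pediatric subjects (58 in R+G, 29 in G) will provide approximately 80% power to detect this difference".

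Section 10.3.2 defines two populations: ITT (all randomized, primary for efficacy) and safety (exposed to study drug). Section 10.4.1 still mentions an evaluable population. Section 10.4.4.1 counts as a failure anyone who does not reach hemostasis within 4 minutes. Section 5.6.1 says treatment is "blinded to study subjects but not to the Investigators, the study site personnel, or the Sponsor" study team, and section 9 adds "The eCRF should be filled out by the site within 48 hours after a visit".

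**The concern.** The replacement wording reads as if it were written for a population that drops untreated subjects. Under ITT nobody is dropped, so replacement enlarges the analysis set instead of restoring it. With one randomized but untreated subject, 87 treated means 88 randomized, which is over the synopsis limit. The power condition has no threshold, and nobody is named to apply it.

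The people running the trial know the allocation, and the primary outcome is visible within minutes. If they could add subjects after 87 in the light of results, the final sample size would depend on the data and the 5% level would not be protected.

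**Working it through.** **The plan's own figure.** Inputs from section 10.1: 0.87 and 0.60, 58 and 29 subjects, two-sided 0.05, chi-square test.
- Pooled rate = (58×0.87 + 29×0.60)/87 = 0.78.
- Null standard error = √[0.78×0.22×(1/58 + 1/29)] = 0.0942.
- Alternative standard error = √[0.87×0.13/58 + 0.60×0.40/29] = 0.1011.
- Power = Φ[(0.27 − 1.96×0.0942)/0.1011] = Φ(0.844) = 80.1%.

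Exact enumeration of the uncorrected chi-square test gives 81.3%. The stated 80% is right, with no allowance for untreated subjects.

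**Withdrawal after treatment.** Hemostasis assessment ends at 5 minutes at the latest (section 6.2.2), and data from withdrawn subjects are retained (section 4.4). A later withdrawal takes nothing out of the powered comparison, so the power condition is idle for these subjects. Deleting it would change no primary result.

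**One randomized, untreated subject.** This subject is also withdrawn, stays in ITT and counts as a failure. With 58 and 29 kept, exact power becomes 75.9% if the subject is in the Raplixa arm and 86.2% if in the control arm, against 81.3% with none. So the power condition is not empty for these subjects, and not every single loss lowers power. The unconditional sentence in 4.4 already permits this replacement.

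**Replace, or stop at 87?** Assume an equal share u untreated in each arm. The documents give no rate. The success rates become 0.87(1−u) and 0.60(1−u). Replacing until 87 are treated gives an ITT total of 87/(1−u).

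| u (assumed) | Power, ITT held at 87 | ITT total if replaced | Power if replaced |
|---|---|---|---|
| 0% | 80.1% | 87 | 80.1% |
| 5% | 72.1% | about 92 | 74.2% |
| 10% | 64.2% | about 97 | 68.7% |

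For example, at u = 5% with 87 held: Φ[(0.2565 − 1.96×0.0996)/0.1045] = 72.1%. Replacement gains 74.2 − 72.1 = 2.1 points at 5% and 68.7 − 64.2 = 4.5 points at 10%. Neither option restores 80%.

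**Type I error.** If replacement ignores outcome, there is no inflation. The hypothetical worst case is a test after each added subject, with a claim at the first significant result. It assumes no true difference, a success rate of 60% to 78% in both arms, 2:1 blocks of three and the windows shown. The documents give neither the blocks nor the windows.

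| Subjects at which a test is made | Two-sided error, chi-square | Two-sided error, Wald test of the unadjusted logistic model |
|---|---|---|
| 87 only | 5.1–5.4% | 4.1–5.0% |
| 87 to 88 | 5.5–5.8% | 4.4–5.3% |
| 87 to 90 | 6.2–6.5% | 5.1–6.1% |
| 87 to 92 | 6.8–7.0% | 5.5–6.7% |

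Section 10.4.4.1 plans logistic regression without naming the test statistic. Wider windows would give larger figures, so these are illustrations and not a ceiling.

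**The case for a change.** The best argument for a change is that it costs almost nothing. One definition of 87, no replacement after treatment and a single rule for untreated subjects would take any question about the final sample size off the table. Only subjects are blinded, nobody is named to decide on replacement, and a team that knows the allocation needs no formal interim analysis to see how results are running.

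Part of this stands. The counts do not agree, the decision-maker is unnamed, and the rule for untreated subjects is discretionary.

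Three things limit it:
- Replacement needs a subject who was actually untreated or withdrawn. The envelope is opened only once a suitable bleeding site is found and the surgeon is ready, and failures of the intra-operative criteria before that are screen failures (section 6.2.2). Few cases should arise, although the documents give no rate.
- The current plan contains no efficacy interim analysis, and the summary of changes says that none will be performed. Prompt data entry is not access to a pooled comparison. That unblinded staff would steer the sample size is inference.
- Stopping at 87 randomized is not purely a wording change, because it gives up the small power gain shown above. Automatic replacement goes over the synopsis limit. Either choice gives something up.

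**Conclusion.** The mismatch is real, but it does not call for a change to the plan. Run as written, the trial still compares all randomized subjects, with untreated ones counted as failures. Discretion over replacement affects how many are analysed, not which randomized subjects are kept. The power condition is idle for treated subjects and redundant for untreated ones. Replacing or not replacing is a fair trade-off worth 2.1 to 4.5 points of power at assumed untreated rates of 5% to 10%.

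The synopsis limit, against the approximate counts in sections 3.1, 4.1 and 10.1, is a difference of wording that a few extra subjects would expose. The evaluable population in section 10.4.1 is a clerical leftover that affects only the baseline tables, and an analyst would read it as ITT.

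This conclusion rests on two readings. Replacement is taken to be made without regard to outcome. The specific failure rule in 10.4.4.1 is taken to govern untreated subjects over the general exclusion of missing data in 10.3.4. If replacement did follow outcome, the level would not be protected, by roughly one percentage point for three added subjects under the chi-square test.
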